2. STUDY OBJECTIVE

To assess the safety, tolerability and efficacy of two different doses of istaroxime (0.5 and 1.0 $\mu g/kg/min$) in comparison with placebo, including cardiovascular and renal tolerability, as well as changes in biological markers such as N-terminal prohormone brain natriuretic peptide (NT-proBNP) and troponin T (cTnT), in two cohorts, Chinese and Italian /Caucasian patients with Acute Decompensated Heart failure.

In all the Italian patients and in a subset of Chinese patients pharmacokinetics and metabolism of istaroxime shall also be studied.

3. STUDY DESIGN

This is a phase II, multicenter, randomized, double-blind, placebo-controlled, parallel group study.

96 Chinese patients and 24 Italian patients will be randomly assigned to one of two doses of istaroxime or placebo in a 2:1 ratio within two sequential cohorts of 60 patients each.

This 31-day study includes a screening period (Days -1), a treatment period (Day 1), a post-treatment period (Days 2-4), and a follow-up period (which includes one patient visit on Day 30).

When a patient is considered fully eligible (i.e. s/he fulfills all the inclusion criteria and does not meet any exclusion criteria as stipulated), the patient will be randomized. Treatment details are presented below:

Cohort I: 0.5 µg/kg/min istaroxime or placebo (40 patients randomized to istaroxime 0.5 µg/kg/min group and 20 patients randomized to placebo group).

Istaroxime 0.5 μ g/kg/min (30 μ g/kg/h) continuous i.v. infusion for 24 hours **not exceeding 72** mg per 24 hours for patients with body weight > 100 kg

Cohort II: 1.0 μ g/kg/min istaroxime or placebo (40 patients randomized to istaroxime 1.0 μ g/kg/min group and 20 patients randomized to placebo group).

Istaroxime 1.0 μ g/kg/min (60 μ g/kg/h) continuous i.v. infusion for 24 hours **not exceeding 144** mg per 24 hours for patients with body weight > 100 kg

Escalation to the next dose (second cohort) will occur after completion of the first cohort and determined by the evaluation of the safety data performed by the Data Safety Monitoring Board.

4. STUDY POPULATION

A total of 96 Chinese and 24 Italian patients hospitalized with ADHF not requiring inotropic therapy at inclusion into the study (according to the opinion of the Investigator) and not presenting signs and/or symptoms of severe low output state or peripheral hypo perfusion will be randomized.

To be included into the study, patients have to fulfill eligibility criteria both at their admission to the hospital (screening criteria) and just prior to randomization (randomization criteria).

4.1 Inclusion criteria

Patients who fulfill the following inclusion criteria at screening will be considered for the study:

- 1. Signed informed consent;
- 2. Male or female patients 18-85 years (inclusive);

- 3.Admission for a recurrent ADHF episode with dyspnea at rest or minimal exertion and need of intravenous diuretic therapy (≥ 40 mg iv. furosemide);
- 4. Systolic blood pressure between 90 and 125 mmHg (limits included) without signs or symptoms of hypoperfusion including cardiogenic shock, cold extremities and peripheral vasoconstriction, oliguria/anuria, signs of cerebral hypo-perfusion such as confusion;
- 5. Left ventricular (LV) Ejection fraction (EF) \leq 40 % measured by 2D-Echocardiography
- 6. E/Ea ratio > 10
- 7. BNP \geq 350pg/mL or NT-pro-BNP \geq 1400 pg//mL;
- 8. Adequate echocardiography window (defined as visualization of at least 13/16 segment of the left ventricle);

4.2 Exclusion criteria

Any of the following criteria established **at screening** would render a patient ineligible for the study:

- 1. Pregnant or breast-feeding women (women of child bearing potential must have the results of a negative pregnancy test recorded prior to study drug administration)
- 2. Current (within 6 hours prior to screening), during the screening or planned (if the patients was treated with dopamine or nitrates iv infusion) (through the completion of study drug infusion) treatment or within 12 hours prior to screening if the patient was treated with other iv. vasodilators or other inotropic agents and vasopressors,
- 3) Current or need of mechanical support (intra-aortic balloon pump, endotracheal intubation, mechanical ventilation, or any ventricular assist device),
- 4. Ongoing treatment with oral digoxin. Patient treated with digoxin cannot be randomized. (However, if digoxin treatment has been stopped during the last week before signing informed consent form and the digoxin plasma level is < 0.5 ng / ml, patient may be randomized; if the patients have stopped digoxin for more than one week before signing informed consent form, it is not necessary to test the plasma level of digoxin.)
- 5. History of hypersensitivity to the study medication or any related medication;
- 6. Diagnosis of cardiogenic shock within the past month;
- 7. Acute coronary syndrome or stroke within the past 3 months;
- 8. Coronary artery bypass graft or percutaneous coronary intervention within the past month or planned in the next month;
- 9. Primary hypertrophic or restrictive cardiomyopathy or systemic illness known to be associated with infiltrative heart disease;
- 10. Cor pulmonale or other causes of right-sided HF not related to left ventricular dysfunction;
- 11. Pericardial constriction or active pericarditis;
- 12. Atrial fibrillation with marked irregularities of heart rhythm (Inclusion criteria 8 can not be met);

- 13. Life threatening ventricular arrhythmia or ICD (implantable cardioverter defibrillator) shock within the past month;
- 14. Presence of a CRT (cardiac resynchronization therapy), ICD or pacemaker devices implanted within the past month;
- 15. Valvular disease as the primary cause of HF (except those corrected by surgery without obstruction in left ventricle output);
- 16. Heart rate > 120 bpm or < 50 bpm
- 17. Acute respiratory distress syndrome or ongoing sepsis;
- 18. Fever $>38^{\circ}$
- 19. History of bronchial asthma or porphyria;
- 20. Donation or loss of blood equal to or exceeding 500 mL, during the 8 weeks before administration of study medication;
- 21. Positive testing for HIV, Hepatitis B and/or Hepatitis C with abnormal liver functions;
- 22. Participation in another interventional study within the past 30 days;
- 23. The following laboratory exclusion criteria, verified based on results obtained within the last 24 hours of hospitalization:
 - a. Serum creatinine > 3.0 mg/dl ($> 265 \mu \text{mol/L}$);
 - b. Aspartate aminotransferase (ASAT) or alanine aminotransferase (ALAT) > 3 x upper limit of normal,
 - c. Hemoglobin (Hb) < 10 g/dL,
 - d. Platelet count $< 100,000/\mu L$,
 - e. Serum potassium > 5.3 mmol/L or < 3.8 mmol/L,

(Note:

- 1. All the hematology and biochemistry results obtained within the past 24 hours before signing ICF can be used as baseline without retesting the patients.
- 2. For HIV, HBV, HCV, T3, T4, TSH, results obtained within one week before the patient signed informed consent form can be accepted.)

5. STUDY PRODUCTS AND DOSE REGIMEN

5.1 TEST DRUG

5.1.1 ISTAROXIME

Name: Istaroxime

Composition: Istaroxime 10 mg, lactose 50 mg, and if needed sodium hydroxide as pH

adjuvant.

Dosage form: Powder for solution for infusion.

Presentation: 10 mg istaroxime glass vial to be reconstituted with 5 ml saline for injection,

according to instructions in leaflet.

Storage Condition: Istaroxime should be stored at room temperature below or equal to 25°C

(77°F) in a secure location. Do not freeze.

Source: provided by CVie Therapeutics Company Limited.

Protocol N°: CVT-CV-002

27

The certificate of analyses will be provided together with the product.

5.1.2 PLACEBO

Composition: Lactose 50 mg, and if needed sodium hydroxide as pH adjuvant.

Dosage form: Powder for solution for infusion.

Presentation: Glass vial to be reconstituted with 5 ml saline for injection, according to

instructions in leaflet.

Storage condition: Placebo should be stored at room temperature below or equal to 25°C (77°F)

in a secure location. Do not freeze

Source: provided by CVie Therapeutics Company Limited.

The certificate of analyses will be provided together with the product.

5.2 Drug Blind Code

The computer generated randomization list stratified by centre and atrial fibrillation (Yes/No) will be prepared via a computerised method. Starting from the lowest number provided, in each center and and atrial fibrillation, at Day 1, patients will be sequentially assigned to the next randomization number, following the order in which they present themselves for the study. The investigator will keep the code break envelopes in a locked, secure storage facility.

A code break envelope can only be opened in an emergency situation (mainly SUSAR occurrence) where the investigator considers it essential to know which treatment the subject was taking. If possible, it is recommended that the investigator contacts the Sponsor before opening an envelope. The monitor shall be promptly notified when a treatment code envelope is opened. The investigator shall provide a certified explanation of why the treatment code was opened in the Case Report Form for the subject or directly on the opened treatment code envelope.

IMPORTANT: The randomization codes will only be disclosed to the laboratory in charge of the bioanalytical assay (plasma and urine PK assessment) of istaroxime and its metabolites, in order to prevent analyses of samples from patients who have received placebo. This laboratory will re-code identifiers of patients, allowing only to differentiate but not to identify the patients, in order to maintain blinding integrity for the other assessments of the study, until database lock. PK results will be maintained separate from the electronic CRF data until database lock at study completion.

Emergency Un-blinding: 1) Un-blinding condition: any emergencies of unknown origin that occur to the subject during the trial, should find out the medication type, or the subject asks to quit and wants to know the medication type; 2) Un-blinding register: the principle investigator opens and reads the emergency letter of corresponding number, recording the reading date and reason in detail, and signs his/her name; 3) Un-blinding disposal: once the emergency letter is **Protocol N°: CVT-CV-002**

read, the corresponding case is regarded as drop-out.

IMPORTANT: An emergency code break by the Investigator may be authorized only in case of an unexpected serious adverse event (SUSAR), suspected to be related to an investigational product and requiring, according to the Investigator, the knowledge of the study treatment administered. In such a case, the following information must be documented in the e-CRF: reason for code break, date, name, qualification, patient initials and birth date (as recorded in the e-CRF) and electronic signature of the person who requested the code break. At completion of the study, all emergency code breaks tracked by the e-CRF will be checked for verification of the blinding integrity.

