5.4 Emergency Envelope/Emergency Unblinding Card

Emergency envelope is prepared for SAE happening, one opens the envelope to rescue in time, and avoid overall un-blinding. "A randomized, double-blind clinical study of Istaroxime", and the randomization number are printed on the envelopes. The emergency envelope draft is as follow:

Double-	blind clinical study emergency	
Un-blinding record Drug Randomization No.: Study project: A randomized, double-blind clinical study of Istaroxime		
_	Therapeutics Company Limited	
	esponsible Sites: XX	
The subject of the	nis Randomization No. is randomly divided into:	
	Test group: Istaroxime 0.5 mcg/kg	
	Test group: Istaroxime 1.0 mcg/kg	
	Control group: Placebo	
Reason for emergency unblinding:		
Study center:		
Signature of investigator: Date:		
Signature of principal investigator: Date: Note: the case should withdraw from the study after emergency un-blinding		

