5.5 Drug Distribution

Registration: All drugs of each site will be stored in one place and managed by a specially-assigned person. The distribution and reclaiming should be registered.

Sequence: the investigator obtain the random no. and drug no. of the subject according to the visiting sequence of the qualified subjects in each study center, and the drug administration office dispense the study drugs of corresponding drug no.

Distribution: The subjects are randomized to the test group (istaroxime) and control group (placebo) in a ratio of 2:1. All study drugs are accompanied by emergency envelopes of corresponding numbers and the emergency envelopes are kept by the principal investigator in attending site.

The drugs should be given to the subjects according to their drug numbers, and shouldn't be chosen. The random numbers should remain unchanged during the study. Each subject will be provided with a random number and sufficient study drugs. The investigator should fill in the Drug Distribution Registration Form exactly in time.

Storage: The study drugs are stored, administrated and distributed by each site. The drugs should be stored hermetically in the shade.

Remaining Drugs: If the drugs remain because patients do not take them on time, or quit midway, or the treatment changes, the drugs should be reclaimed and recorded in detail.

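### Protocol Section 5.2 gives code-break conditions that cannot all hold, and one of them unblinds a patient who quits with no medical need

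*Protocol*

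**What the plan says.** Section 5.2 of the protocol states the grounds for breaking the code in three places.

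- **Opening rule.** An envelope "can only be opened in an emergency situation (mainly SUSAR occurrence"), and only where the investigator considers the code essential. Where possible, "it is recommended that the investigator contacts the Sponsor before opening an envelope". The monitor must be told promptly. The explanation goes "in the Case Report Form for the subject or directly on the opened treatment code envelope".
- **Emergency un-blinding paragraph.** The grounds are an emergency whose cause is not known, "or the subject asks to quit and wants to know the medication type". The principal investigator opens the letter, records the date and reason, and signs. The patient then counts as a drop-out.
- **Second IMPORTANT note.** A break "may be authorized only in case of an unexpected serious adverse event (SUSAR"). The event must also be suspected to be drug-related and, in the investigator's view, require the code. In that case a set of items is entered in the e-CRF. At study completion, "all emergency code breaks tracked by the e-CRF will be checked for verification of the blinding integrity".

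Section 5.4 describes the purpose a fourth way: "Emergency envelope is prepared for SAE happening". Its printed form asks for the reason, the centre, and dated signatures of the investigator and the principal investigator, and it says that the patient should withdraw. Under Section 5.5, "the emergency envelopes are kept by the principal investigator in attending site".

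**The concern.** A site facing a request to open an envelope needs one answer, and Section 5.2 can give opposite ones. Two things are at stake.

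The first is the blind. The quit-and-ask ground requires neither an emergency nor a medical reason, yet the person who opens the code is the principal investigator. Both of the other rules exclude that ground.

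The second is emergency access. Taken literally, the SUSAR-only note forbids a break that the opening rule would allow, namely when the code is essential but the emergency is expected or attributed to something other than the drug.

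The recording rules also differ, so the check on blinding at the end of the study may not see every break.

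**Working it through.** The documents give no figure on this point, so the check sets the texts side by side.

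**Grounds for a break.** Each case is read against the three texts of Section 5.2.

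| Case | Opening rule | Un-blinding paragraph | SUSAR-only note |
|---|---|---|---|
| Patient quits and asks, no emergency | No | Yes | No |
| Emergency of unclear cause, drug not suspected | Yes, if code essential | Yes | No |
| Emergency from an expected serious event | Yes, if code essential | Only if cause unknown | No |
| Emergency attributed to another cause | Yes, if code essential | No | No |
| SUSAR emergency, code needed | Yes | Only if cause unknown | Yes |

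The opening rule and the note are both worded as exclusive, so the quit-and-ask ground contradicts each of them. The opening rule treats a SUSAR as the main case and the note treats it as the only case, so those two contradict each other. Section 5.4 is wider than the note, because it covers serious events without requiring them to be unexpected or related. No text available to this review ranks these statements. Section 10.5 and the Operation Manual could not be seen.

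**Recording.**

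- Opening rule: the CRF or the opened envelope. Section 13.1 makes the CRF electronic, so the gap is the envelope-only option.
- Un-blinding paragraph: a signed record of date and reason, with no place stated.
- Note: e-CRF items required, but only for the SUSAR case it describes.
- End-of-study check: only breaks tracked in the e-CRF.

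A break on the quit-and-ask ground can therefore comply with Section 5.2's recording rules and still fall outside the check.

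**What an unblinded quitter can affect.**

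1. The principal investigator learns the treatment.
2. If the patient left because of an adverse event, Section 10.1 has the investigator follow that event until recovery.
3. Section 10.3 has the investigator rate its relation to the drug. One listed ground for Certainly unrelated is that no test drug was taken, and a code showing placebo would supply that ground.
4. SAP Section 6.4 counts every other rating as an adverse drug reaction.

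A rating made after the break is therefore made with knowledge of treatment. If the rating was made before the break, this route is closed.

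**The case against.** The strongest reply is that this is loose drafting with little behind it. The opening rule and Section 5.4 both show that wider emergency access was intended, and the infusion can be stopped without the code, as Section 5.7 directs when a rescue inotrope is needed. This stands. A reader might infer that the plan denies emergency unblinding to patients who need it. Only a literal reading of one sentence against two others gives that result, so the safety risk is limited.

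A second reply is that the three texts describe separate routes, paper envelopes for the first two and the e-CRF for the note. The documents do not say so. The note speaks of any emergency code break by the investigator, who also holds the envelopes. Its wording does suggest that someone authorises a request, but no one is named, so neither the presence nor the absence of a veto can be claimed.

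A third reply is that breaks do not go unrecorded, and this also stands. Sponsor contact is recommended, the monitor must be notified, the envelope form carries two dated signatures, and the patient becomes a drop-out, with reasons for discontinuation tabulated under SAP Section 7.5. Section 15 also requires unified training. A reader might infer that a quit-and-ask break leaves no trace. What the text shows is narrower: the end-of-study check need not cover it. None of these controls says which ground is valid.

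Finally, a reader might put a size on the effect. Pooled placebo is 20 + 20 = 40 patients, so one re-rated patient would move the placebo adverse-drug-reaction rate by 1/40 = 2.5 percentage points. The documents do not support using that as a measure of the harm. It needs a placebo patient who quits because of an adverse event, asks for the code, has not yet been rated, has no other adverse drug reaction, and is then rated Certainly unrelated. Re-rating can follow any break, including one in a true emergency, and adverse drug reactions are only summarised, not tested.

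**Conclusion.** The conflict is real and rests on the current wording alone. The main consequence is avoidable unblinding of patients who quit, some of whom the unblinded investigator may still follow and rate, together with a blinding check that can miss breaks explained only on the envelope. The risk to emergency care is secondary and limited.

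No size can be given, because the documents state no expected number of code breaks. No alpha, power, sample-size figure or planned analysis changes. The conclusion assumes that nothing in Section 10.5 or the Operation Manual ranks the rules. The point about relatedness further assumes that the rating has not been made when the code is opened. This is a change the sponsor should make. It is not a threat to the trial's validity.

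**What to change.** - Use one rule in Sections 5.2 and 5.4: the code may be broken when the investigator judges that knowing the treatment is essential to manage a medical emergency. Prior contact with the sponsor is recommended, not required.
- Delete the quit-and-ask ground from the un-blinding paragraph.
- Replace the SUSAR-only restriction in the note with the same rule.
- Record every code break in the e-CRF with the items the note already lists, even when the reason is also written on the envelope, so that the end-of-study check covers all breaks. Keep the monitor notification.
- Where feasible, record the relatedness rating before the code is opened. Deleting the quit-and-ask ground alone does not protect the rating when the break is a proper one.

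The cost is a protocol amendment, with the ethics approval that Section 17 requires, and a notice to sites. The printed envelope form states no condition for opening, so it need not be reissued. Visits and analyses do not change.

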5.3 Drug packaging

The test drugs and placebo are packaged in the glass vials of identical size.

The test drug Istaroxime (10 mg test drug + 50 mg lactose) and the placebo (50 mg of lactose) are contained in glass vials of 7 ml each as lyophilized powder.

Dummy: Packaging dummy technique will be adopted as follows:

The investigational drug and placebo will be provided as kits containing 4 study boxes. Each study box for each patient will be used for 6 hours iv. infusion, for a total of 24 hours infusion for the 4 boxes. Each study box for the 6 hour infusion will contain 4 glass vials of 7 ml.

According to the treatment (test drug-istaroxime or placebo) and to the dose (test drug-istaroxime: 0.5 or 1.0 mcg/kg/min) the 6-hour box will contain:

- 1. Istaroxime (0.5 mcg/kg/min):
 - 2 glass vials of 7 ml containing lyophilized powder of test drug (10 mg) + 50 mg of lactose
 - 2 glass vials of 7 ml containing lyophilized powder of placebo (50 mg of lactose)
- 2. Istaroxime (1.0 mcg/kg/min):
 - 4 glass vials of 7 ml containing lyophilized powder of test drug (10 mg) + 50 mg of lactose
- 3. Placebo
 - 4 glass vials of 7 ml containing lyophilized powder of placebo of istaroxime (50 mg of lactose)

All these boxes will be uniformly packaged and the vials will be tightly covered by study special label. The clinical study approval document number, drug serial numbers, expiry date, usage method and attentions should be stated on the labels.

Packaging: External packing and inner packing, inner packing is 4 glass vials (see above) while external packing is a white box. Outside the box and vials are pasted by study special label (refer the contents to the label drafts only for Chinese sites).

1). External packing box label of test drugs and control drug (OK)

Istaroxime injection for AD	HF clinical study
	Approve No.: 2015L00219
Drug No.:	Drug batch.:
Study No.:	EUDRACT No.:
Strength: 10 mg /vial, Lyophilized powder	Expiry date:
Quantity: infusion for 24h, contain 4 small bo	oxes, each with 4 vials
Storage condition: below 25 °C (77°F) room to	emperature, don't freeze
Dose regimen: adjust infusion rate according	to body weight, prepare drug every 6h
Storage temperature: XXX°C.	
Sponsor: CVie Therapeutics	Company Limited
To be used only for clinical trials. Keep out of	children's reach. Please return the
remaining. drugs	n timely

2). Inner packing box label of test drugs and control drug

Istaroxime injection for ADHF clinical study	
	Approve No.: 2015L00219
Dru	ug No.: Drug batch.:
Stu	ldy No.: EUDRACT No.:
Str	ength: 10 mg /vial, Lyophilized powder Expiry date:
Qu	antity: infusion for 6h, 4 vials per box
Sto	orage condition: below 25°C(77°F) room temperature, don't freeze
Do	se regimen: adjust infusion rate according to body weight, prepare drug every 6h
	Sponsor: CVie Therapeutics Company Limited
To be used only for clinical trials. Keep out of children's reach. Please return the	
	remaining. drugs in timely

30

3). Vial label of test drugs and control drug

Istaroxime injection for	or ADHF clinical study	
	Approve No.: 2015L00219	
Drug No.:	Drug batch.:	
Study No.:	EUDRACT No.:	
Strength: 10 mg /vial, Lyophilized power	der Expiry date:	
Storage condition: below 25 °C (77°F) roo	om temperature, don't freeze	
Dose regimen: adjust infusion rate according to body weight, prepare drug every 6h		
Sponsor: CVie Therapeu	ıtics Company Limited	
To be used only for clinical trials. Keep out of children's reach. Please return the		
remaining. dr	ugs in timely	

